# Continuing Review

## Basic Info

Confirmation Number: **chbgaide**  
Protocol Number: **828183**  
Created By: **[name]**  
Principal Investigator: **[name]**  
Protocol Title: **Use of A Telehealth Intervention to Decrease Readmissions in Cirrhosis: A Randomized Controlled Trial**  
Short Title: **Telehealth RCT in Cirrhotics**  
Protocol Description: **The proposed study is a randomized controlled trial comparing a simple telehealth intervention implemented after hospital discharge to standard of care for reducing hospital readmissions. All cirrhotic patients admitted to the Hepatology service at The Hospital of the University of Pennsylvania will be randomized to one of the two arms outlined above. Patients will be followed for 90 days. Rates of 30 and 90 day readmission will be compared between the groups.**  
Submission Type: **Social and Biological Sciences**  
Application Type: **FULL**

## PennERA Protocol Status

Approved (No CR)

## Level of IRB Review Required

Expedited Review

**The following documents are currently attached to this item:**

*There are no documents attached for this item.*

## Summary of protocol modifications approved since last continuing review

Please provide a description of changes which have been reviewed and approved by the IRB since the last continuing review.

## Subject Enrollment

**Target subject enrollment at Penn**

0

**Target enrollment at other centers (multi-center study)**

0

**Number of subjects enrolled at Penn since the study was initiated**

0

**Actual enrollment at participating centers**

0

**Number of subjects enrolled at Penn since the last continuing review**

**Total number of subjects who provided consent**

0

**Number of subjects determined to be ineligible**

0

**Number of subjects currently active/on study**

0

**Number of subjects lost to follow-up**

0

**Number of subjects no longer participating for other reasons**

0

**Number of subjects who have completed the study**

0

**Number of subjects who have withdrawn from the study**

0

***Race:***

**American Indian or Alaskan Native**

0

**Asian**

0

**Black or African American**

0

**Native Hawaiian or Pacific Islander**

0

**White**

0

**Other**

0

**Unknown or Not Reported**

0

***Ethnicity:***

**Hispanic or Latino**

0

**Not Hispanic or Latino**

0

***Gender***

**Male**

0

**Female**

0

**Other**

0

**Unknown / Not Reported**

0

**Total**

0

***Vulnerable Populations***

**Has your study enrolled pregnant woman?\***

No

**Has your study enrolled prisoners?\***

No

**Has your study enrolled children?\***

No

***Subject Withdrawal***

**How many subject voluntarily withdrew from the study?**

0

**How many subjects were withdrawn from the study at the request of the PI/Co-PI?**

0

**Number of subjects withdrawn due to adverse events/unanticipated problems**

0

**Subject withdraw reason\***

If subjects voluntarily withdrew or were withdrawn, please indicate the reasons.

**Issues with recruitment/retention, informed consent, or other issues**

If applicable, please provide a brief summary of any difficulty you experienced obtaining/retaining subjects or obtaining informed consent during the entire approval period. Additionally, please indicate if there have been any complaints about the research.

**Informed Consent Process\***

Recognizing that informed consent encompasses much more than a form or document there are a number of methods employed to educate a potential subject as to what is involved in a particular research project. The forms used are one method for documenting the informed consent process. Is written informed consent required for this project?

No

**Is written HIPAA authorization required?\***

No

**New Findings**

**Significant preliminary observations/interim findings**

Have there been any significant preliminary observations/interim findings during the past approval period. If yes, please describe below.

**DMC or DSMB exists\***

Does a data monitoring committee (DMC) or data and safety monitoring board (DSMB) exist?

No

**DMC or DMB Report Status**

**The following documents are currently attached to this item:**

*There are no documents attached for this item.*

**Multi-site trial summary**

If this study is a multi-site trial, provide a narrative summary of any relevant reports that have been received in the past year, regardless of whether the report has been previously submitted to the IRB.

**Disclosure of Significant Financial Interests\***

Investigators (persons responsible for the design, conduct or reporting of this research protocol) must disclose any of the following financial interests / relationships with any entity that sponsors, provides support, or otherwise has a financial interest in the conduct or outcome of this research protocol (Outside Organization): Payments received for the past 12 months from a publicly traded Outside Organization for personal services (e.g., consulting, lecturing / speaking, service on the Scientific Advisory Board) plus the value of any current equity that when aggregated exceeds \$5,000 Payments received for the past 12 months from a non-publicly traded Outside Organization for personal services that in total exceed \$5,000, or having any equity interest Membership on the governing board of any Outside Organization, including service on its board of directors, or having a position of authority or responsibility to act in its best interests, including being an officer, manager, partner, or limited liability company member with management responsibility Investigators must also disclose any financial interest in a drug, device or other product or a competing product (IP rights), regardless of whether the IP has been patented, licensed, or assigned to the Penn, if such IP is being tested, evaluated, or developed in, or if its commercial value could be affected by, this protocol. Investigators are not required to disclose equity in mutual funds and retirement accounts, as long as the Investigator does not directly control the investment decisions made in these vehicles. Does any Investigator (or his or her spouse or dependent children) have a SIGNIFICANT FINANCIAL INTEREST, as defined above?

No

**Penn Intellectual Property\***

To the best of the Principal Investigator's knowledge, does this protocol involve the testing, development or evaluation of a drug, device, product, or other type of intellectual property (IP) that is owned by or assigned to the University of Pennsylvania?

No

**Certification**

I have reviewed the Financial Disclosure and Presumptively Prohibited Conflicts for Faculty Participating in Clinical Trials and the Financial Disclosure Policy for Research and Sponsored Projects with all persons who are responsible for the design, conduct, or reporting of this research; and all required Disclosures have been attached to this application.

Yes

**Study Completion / Expiration**

**Study Complete\***

Is this study complete?

No

**Study Complete - Explanation**

If study is complete Please indicate why (eg., research related activities and data analysis are complete, required number of subjects reached, issues with protocol safety, etc.)

**The following documents are currently attached to this item:**

*There are no documents attached for this item.*

**IRB Approval Expired\***

Has IRB approval for this protocol expired or will it expire before the scheduled IRB review?

No

**Research During IRB Approval Lapse**

If the IRB approval for the protocol has expired or will expire before the scheduled IRB review, confirm that no research related activities occurred/will occur without approval from the IRB unless the PI contacted the Office of Regulatory Affairs and the IRB Executive Chair (or authorized designee) determined that it is in the best interest of subjects to continue during the lapse in IRB approval. For example, in a clinical trial there are (1) subjects who are enrolled but not on intervention, (2) subjects who are on intervention, and (3) subjects who have completed the intervention phase and are in follow up. The IRB Executive Chair must evaluate each of these groups separately regarding continuation of participation in the research after IRB approval has expired. Have any research activities occurred, or will any research activities need to occur, during the lapse in IRB approval?

No

**Unanticipated Problems\***

Since the last IRB Review, have there been any unanticipated study related events that have not been previously reported to the IRB?

No

**The following documents are currently attached to this item:**

*There are no documents attached for this item.*

**Adverse Events\***

Since the last IRB review, has the profile of adverse events (in terms of frequency, severity, or specificity) changed from previous experience or as documented in the research protocol, informed consent document, or investigator's brochure?

No

**The following documents are currently attached to this item:**

*There are no documents attached for this item.*

***Documents attached from the IRB protocol application.***

**The following documents are currently attached to this item:**

**Informed consent form (livebettercirrhosisinformedconsent\_03.08.2018.pdf)**

**Informed consent form (livebettercirrhosis\_verbal\_consentclean17april2018.pdf)**

**List of Documents Details**

Please detail the rationale for why any of the above documents are not attached to the submission (i.e. No Investigator's Brochure, Protocol, or Consent Forms are utilized for this protocol).

# Protocol Details

## Resubmission\*

Yes

**Responsible Org (Department/School/Division):**

4237 - DM-Gastroenterology

**Disclosure of Significant Financial Interests\***

Does any person who is responsible for the design, conduct, or reporting of this research protocol have a **FINANCIAL INTEREST**?

No

**Penn Intellectual Property\***

To the best of the Principal Investigator's knowledge, does this protocol involve the testing, development or evaluation of a drug, device, product, or other type of intellectual property (IP) that is owned by or assigned to the University of Pennsylvania?

No

**Certification**

I have reviewed the *Financial Disclosure and Presumptively Prohibited Conflicts for Faculty Participating in Clinical Trials* and the *Financial Disclosure Policy for Research and Sponsored Projects* with all persons who are responsible for the design, conduct, or reporting of this research; and all required Disclosures have been attached to this application.

Yes

## Social and Biological Sciences

**Study Instruments**

Discuss the particulars of the research instruments, questionnaires and other evaluation instruments in detail. Provide validation documentation and or procedures to be used to validate instruments. For well know and generally accepted test instruments the detail here can be brief. More detail may be required for a novel or new instrument. For ethnographic studies identify any study instruments to be used (i.e. for deception studies) and describe in detail where, when and how the study will be conducted and who or what are the subjects of study. Note: For more information on how to conduct ethical and valid ethnographic research, follow the link [For oral histories or interviews provide the general framework for questioning and means of data collection.](#) If interviews or groups settings are to be audio taped or video taped describe in detail the conditions under which it will take place. Include a copy of any novel or new test instruments with the IRB submission.

Way to Health is a web-based platform that automates many functions necessary for conducting randomized controlled trials of health behavior interventions. The platform, designed by faculty and staff at the Leonard Davis Institute's Center for Health Incentives and Behavioral Economics (CHIBE), is utilized to create an efficient, scalable, and low cost way to test behavioral interventions using a technology that can be deployed anywhere. The Way to Health platform will be utilized to support the randomized controlled trial herein proposed. A Way to Health Site will be constructed for this study based on observations and refinements of study materials utilized for a pilot study conducted by the research group in this patient population, the platform will be utilized to store demographic data, document consent, conduct randomization procedures, obtain elicited biometric data and provide clinical monitoring based on received biometric data for participants. Daily SMS prompts as mapped out by the study team (see flow diagrams attached as supporting materials) will be sent to enrolled participants randomized to the intervention arm) and a clinical patient liaison will be trained to augment biometric data collected as needed and act on or escalate review of data that may require physician intervention. Additionally, survey data will also be collected through Way to Health on a daily basis. Any concerning symptoms elicited by the daily surveys will also be reviewed by the clinical patient liaison and if necessary communicated to the participants' clinician as needed via phone, email or text. The telehealth monitoring provided by the Way to Health Platform will be utilized to document changes in daily weights, symptoms of hepatic decompensation (hepatic encephalopathy, volume overload, and/ or bleeding) and adherence with prescribed medication regimens. SMS messages will be sent to participants randomized to the intervention arm twice daily, AM messages including an assessment of weight and a rotating survey question to assess other concerning symptoms and a PM message to review medication adherence. Once weekly, an assessment of confusion using a number connection test will be administered. Additional surveys to be administered will include the following: pre and post quality of life assessment (SF 36 and the chronic liver disease questionnaire, CLDQ, see attached), and an assessment of patient satisfaction (survey) administered at the beginning, middle and end of the intervention.

**Group Modifications**

Describe necessary changes that will or have been made to the study instruments for different groups. No changes will be made to study instruments based on differential group assignment. No SMS messages will be provided to those participants randomized to the usual care arm until completion of

their observation period. To allow all participants to experience the intervention, the usual care arm subjects will be offered 90 days of telehealth monitoring after completion of the study. Additionally, the program and quality of life surveys required for study participation are identical regardless of group assignment.

#### **Method for Assigning Subjects to Groups**

Describe how subjects will be randomized to groups.

Permuted block randomization will be utilized to randomize patients to the intervention and usual care arms, maintaining a 1:1 ratio as determined most efficient for obtaining the necessary sample size but decreasing the ability of study staff to know to which group a new participant will be assigned. All randomization procedures will be executed on the Way to Health Platform.

#### **Administration of Surveys and/or Process**

Describe the approximate time and frequency for administering surveys and/or evaluations. For surveys, questionnaires and evaluations presented to groups and in settings such as high schools, focus group sessions or community treatment centers explain how the process will be administered and who will oversee the process. For instance, discuss the potential issues of having teachers and other school personnel administer instruments to minors who are students especially if the content is sensitive in nature. Describe the procedure for audio and videotaping individual interviews and/or focus groups and the storage of the tapes. For instance, if audio tape recording is to be used in a classroom setting, describe how this will be managed if individuals in the class are not participating in the study. Explain if the research involves the review of records (including public databases or registries) with identifiable private information. If so, describe the type of information gathered from the records and if identifiers will be collected and retained with the data after it is retrieved. Describe the kinds of identifiers to be obtained, (i.e. names, social security numbers) and how long the identifiers will be retained and justification for use.

All participants randomized will take a pre and post study quality of life assessment (SF-36 and CLDQ, as described previously) and evaluate the program three times during the study period (90 days). Participants randomized to the telehealth intervention arm will also complete surveys / symptom questionnaires on a daily basis through the SMS feature provided through Way to Health, as outlined above. Data will be transmitted directly to the Way to Health platform and stored securely. Identifiers such as name, address, date of birth and social security number will be entered into the platform at enrollment. Only de-identified data will be available for review/ analysis. Additionally, access to the Way to Health Platform is password protected and access to data will be assigned and be commensurate with nature study staff involvement.

#### **Data Management**

Describe how and who manages confidential data, including how and where it will be stored and analyzed. For instance, describe if paper or electronic report forms will be used, how corrections to the report form will be made, how data will be entered into any database, and the person(s) responsible for creating and maintaining the research database. Describe the use of pseudonyms, code numbers and how listing of such identifiers will be kept separate from the research data.

The data will be securely stored on the Way to Health platform, with limitations in access to the PI, [name], and Way to Health staff. At the time of analysis, a deidentified version of the data will be provided to the designated biostatistician/ biostatistical staff for analysis.

#### **Radiation Exposure\***

Are research subjects receiving any radiation exposure (e.g. X-rays, CT, Fluoroscopy, DEXA, pQCT, FDG, Tc-99m, etc.) that they would not receive if they were not enrolled in this protocol?

No

#### **Human Source Material\***

Does this research include collection or use of human source material (i.e., human blood, blood products, tissues or body fluids)?

No

#### **CACTIS and CT Studies\***

Does the research involve Center for Advanced Computed Tomography Imaging Services (CACTIS) and CT studies that research subjects would not receive if they were not part of this protocol?

No

**CAMRIS and MRI Studies\***

Does the research involve Center for Advanced Magnetic Resonance Imaging and Spectroscopy (CAMRIS) and MRI studies that research subjects would not receive if they were not part of this protocol?

No

**Cancer Related research not being conducted by an NCI cooperative group\***

Does this protocol involve cancer-related studies in any of the following categories?

No

**Medical Information Disclosure\***

Does the research proposal involve the use and disclosure of research subject's medical information for research purposes?

Yes

**CTRC Resources\***

Does the research involve CTRC resources?

No

**If the answer is YES, indicate which items is is provided with this submission:**

Modified research informed consent document that incorporates HIPAA requirements

**Use of UPHS services\***

Does your study require the use of University of Pennsylvania Health System (UPHS) services, tests or procedures\*, whether considered routine care or strictly for research purposes?

No

**Primary Focus\***

Clinical Trial (prospectively assigning subjects to health-related interventions to evaluate outcomes)

**Protocol Interventions**

 Sociobehavioral (i.e. cognitive or behavioral therapy) 
 
Drug
 
Device - therapeutic
 
Device - diagnostic (assessing a device for sensitivity or specificity in disease diagnosis)
 
Surgical
 
Diagnostic test/procedure (research-related diagnostic test or procedure)
 
Obtaining human tissue for basic research or biospecimen bank
 
  Survey instrument 
 
None of the above
 

---

**The following documents are currently attached to this item:**

*There are no documents attached for this item.*

### *Department budget code*

400 - 400 - 2 - 014001 - xxxx - 2001 - 0917

### *Funding Sponsors*

Name:	MCCABE FUND
Type:	UPENN Other Non-Profit Organizations

#### **Funding sponsors billing address**

If you have selected a commercial or industry sponsor, please provide the appropriate address and contact information for the Sponsor for the purposes of billing for IRB review fees (initial review, continuing review and convened modification fees apply here). If the Sponsor is not industry/commercial, this information is not necessary to provide with your application.

#### **Funding sponsors gift**

Is this research being funded by a philanthropic gift?  
No

#### **Regulatory Sponsor**

##### **IND Sponsor**

none

400 - 400 - 2 - 014001 - xxxx - 2001 - 0917

##### **Industry Sponsor**

None

#### **Project Funding\***

Is this project funded by or associated with a grant or contract?  
Pending

#### **Sponsor Funding**

Is this study funded by an industry sponsor?  
No

#### **Status of contract**

**The following documents are currently attached to this item:**

*There are no documents attached for this item.*

## Multi-Site Research

### *Other Sites*

No other sites

### **Management of Information for Multi-Center Research**

**The following documents are currently attached to this item:**

*There are no documents attached for this item.*

## Protocol

### **Abstract**

To compare rates of 30 and 90-day readmission of cirrhotic patients to The Hospital of the University of Pennsylvania randomized to telehealth monitoring, as administered by the Way to Health Platform, or usual care. 2. To use a patient centered approach to determine the specific interventions which are most helpful as perceived by patients and have an impact on quality of life. Approximately 426 subjects will be enrolled.

### **Objectives**

#### **Overall objectives**

1. To compare rates of 30 and 90 day readmission of cirrhotic patients to The Hospital of the University of Pennsylvania randomized to telehealth monitoring, as administered by the Way to Health Platform, or usual care. 2. To use a patient centered approach to determine the specific interventions which are most helpful as perceived by patients and have an impact on quality of life.

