#### **Primary outcome variable(s)**

A decrease in readmission rates of cirrhotic patients.

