**Key inclusion criteria**

1. Cirrhotic patients between the ages of 18-80 years old 2. Admitted to the Hospital of the University of Pennsylvania or an outside hospital in the last 30 days 3. Ability to consent for themselves or surrogate can consent. 4. Ability to read and provide informed consent in English. 4. Possess a cell phone and willing to receive text messages.

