### Procedures

All cirrhotics admitted to the Hospital of the University of Pennsylvania between the ages of 18 and 80 will be approached for consent (see attached consent forms in the designated section of the protocol). If patients are missed due to being discharged on the weekend, during a holiday or timing issue, patients may be contacted by phone to enroll in the study. If interested, patients can give verbal consent over the phone or written consent at their following clinic visit. After consent is obtained and information is entered into the Way to Health Platform, the participant will be randomized. During this period of time, the participant will be asked to complete the quality of life assessments/ program surveys. Depending on the group to which they are randomized, those in the intervention group will receive welcome items (scale, stop watch, and binder, all necessary for proper data collection in the intervention group). Those randomized to the usual care arm will receive their standard discharge paperwork. Clinical data (readmissions, reasons for readmissions, and length of stay) will be determined for both groups at 30 and 90 days. The groups will additionally be asked to complete quality of life assessments at the end of the study period and a program assessment in the middle and end of the protocol. Additionally, as assessment of readmission rates will be determined in both groups for another 90 days after the end of the intervention (to determine if the health behaviors learned in the intervention group are durable and to determine if providing the intervention to those in the usual care arm is beneficial even if there is a delay in initiation).

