**Analysis Plan**

The primary analysis will include a comparison of the demographics and clinical data for the intervention group and the usual care group. To determine if there is a difference in the rates of readmission between the groups, univariable logistic regression analysis will be performed. Any predictors which were different between the groups will be used for adjustment in a multivariable logistic regression. We plan to analyze the data at the 6 month mark. If a significant difference is found, given the low cost of the intervention and potential benefits, the study will be stopped and all patients admitted to the hepatology service will be eligible for telehealth monitoring. Data for the secondary outcomes including changes in quality of life and patient satisfaction will be explored.

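### The primary event and its clock are stated inconsistently: whether readmissions to other hospitals count, and whether follow-up includes time before randomization

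*Protocol*

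**What the plan says.** **Which hospital.** Objective 1 (Overall objectives) concerns "readmission of cirrhotic patients to The Hospital of the University of Pennsylvania", and the Abstract repeats it as "rates of 30 and 90-day readmission of cirrhotic patients to The Hospital of the University of Pennsylvania". Other sections name no hospital for the event:

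- Basic Info: "Rates of 30 and 90 day readmission will be compared between the groups".
- Primary outcome variable(s): "A decrease in readmission rates of cirrhotic patients".
- Procedures: "Clinical data (readmissions, reasons for readmissions, and length of stay) will be determined for both groups at 30 and 90 days".
- Analysis Plan: "To determine if there is a difference in the rates of readmission between the groups", followed by a logistic regression.

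**Who is enrolled.** Key inclusion criteria accept a patient who was "Admitted to the Hospital of the University of Pennsylvania or an outside hospital in the last 30 days". Basic Info and Target population describe inpatients of the study hospital's Hepatology service, and Procedures describes cirrhotic inpatients of that hospital.

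**When the clock starts.** Study duration starts follow-up on the day of discharge and ends it 90 days later. Procedures says that patients missed before discharge may be telephoned, and that "patients can give verbal consent over the phone or written consent at their following clinic visit"; randomization follows consent. The Consent Process overview describes recruitment as mainly before discharge, with a telephone attempt within a week of discharge for some patients.

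**The concern.** Two careful readers could count different events for the same primary outcome. One would score a patient readmitted elsewhere as a failure, the other as a success. Such stays are foreseeable, because the eligibility list itself brings in patients who use other hospitals. For those patients the literal objective fits badly: a return to the hospital of the index stay is not an event, and a first admission to the study hospital is not strictly a readmission to it.

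The clock is a second, separate problem. If follow-up runs from discharge and randomization comes days or weeks later, a readmission in the gap is inside the window but cannot have been influenced by the allocated arm. The gap falls early after discharge. Background says that about half of potentially preventable readmissions on this service occur within 10 days.

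The objective, primary outcome, eligibility and start of follow-up are protocol content, so this is not detail that can be left to an analysis plan.

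**Working it through.** **Step 1. Can the plan's own figure be reproduced?** No. The protocol gives 426 subjects (Abstract; Subjects enrolled by Penn Researchers) at 1:1 (Method for Assigning Subjects to Groups), so 426 / 2 = 213 per arm. It states no alpha, power, effect or dropout. Solving backwards, 213 per arm gives 80% power at two-sided 0.05 for 28% vs 16.7%, or for 53% vs 39.5%. Neither pair appears in the protocol, so this does not show how 426 was obtained.

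**Step 2. Effect of missing outside readmissions equally in both arms.**

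Inputs from the protocol (Background): a 30-day rate of 28% at the study hospital, and a 90-day rate of 53% in a 14-center consortium. Background does not say whether either includes outside stays. Both are treated here as all-hospital rates; if they already omit outside stays, the loss is smaller.

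Assumptions: two-sided 0.05; telehealth risk 40% against 53%, or 28% × 0.6 = 16.8% against 28%; share missed m = 0, 10, 20 or 30%, equal in both arms.

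Formulas, with n = 213:

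- Observed risks: a = p0(1 − m), b = p1(1 − m). The observed difference is therefore the true difference times (1 − m).
- Mean risk p̄ = (a + b)/2; s0 = √[2p̄(1 − p̄)]; s1 = √[a(1 − a) + b(1 − b)].
- Power = Φ{[(a − b)√n − 1.96·s0] / s1}.

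Worked line, 53% vs 40%, m = 0: (0.130 × √213 − 1.96 × 0.7054) / 0.6994 = (1.897 − 1.383) / 0.6994 = 0.736, and Φ(0.736) = 0.769.

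| Missed | 53% vs 40%: observed | Difference | Power | 28% vs 16.8%: observed | Difference | Power |
|---|---|---|---|---|---|---|
| 0% | 0.530 / 0.400 | 0.130 | 77% | 0.280 / 0.168 | 0.112 | 79% |
| 10% | 0.477 / 0.360 | 0.117 | 69% | 0.252 / 0.151 | 0.101 | 74% |
| 20% | 0.424 / 0.320 | 0.104 | 60% | 0.224 / 0.134 | 0.090 | 68% |
| 30% | 0.371 / 0.280 | 0.091 | 52% | 0.196 / 0.118 | 0.078 | 61% |

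The assumed effect matters too. At a 53% control risk, a telehealth risk of 38% takes power from 88% to 81/73/64%, and a telehealth risk of 43% takes it from 54% to 47/40/33%.

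Equal loss leaves the type I error at 5%.

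**Step 3. Readmissions before randomization.** Let q be the share of patients readmitted before randomization, and r0 and r1 the later risks, within the window, among the others. The counted risks are q + (1 − q)r0 and q + (1 − q)r1, so the difference is (1 − q)(r0 − r1). Randomization makes q equal in expectation in the two arms. The contrast shrinks, but it is zero when the intervention has no effect. The protocol gives no value for q, so no number is attached.

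**The case against.** The phrase in objective 1 may be no more than loose drafting. The Abstract carries the same sentence, its word order is awkward, and the hospital's name may simply describe the patients. The sections that set the outcome, data collection and analysis do not restrict the hospital, and Procedures applies the same 30- and 90-day determination to both groups. This stands in part: no section says that outside stays are dropped. But none says that they count either, and the only wording that names a hospital points the other way.

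Three stronger readings are tempting, and the documents do not support them:

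- *Outside readmissions will be lost.* That follows only from the literal objective. The share of readmissions going elsewhere is not stated.
- *The treatment estimate is biased.* Unequal capture between arms would bias it, but nothing in the protocol shows that capture differs.
- *Half of all readmissions precede late randomization.* The 10-day figure concerns potentially preventable readmissions only, and post-discharge enrolment is the secondary route.

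It is also fair to say that any power loss depends on the scenario chosen. That is why two base rates are shown; the loss is milder at 28%.

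**Conclusion.** The inconsistencies are certain; their size is not. The protocol leaves open whether the primary event is readmission to the study hospital or to any hospital, admits patients with an outside index stay against its own description of the population, and starts follow-up before some patients are randomized. If 10 to 30% of readmissions went uncounted equally in both arms, power would drop by about 8 to 25 percentage points at a 53% base rate (77% to 69–52%), or about 5 to 18 points at 28% (79% to 74–61%). These figures rest on an assumed effect, alpha and outside share, so they illustrate the stake and do not show that 426 is too small. The clock problem adds dilution of unknown size. The point should be corrected, with moderate confidence in how much it matters in practice.

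**What to change.** **Event.** State in the Abstract, Overall objectives, Primary outcome, Procedures and Analysis Plan that readmission to any acute-care hospital counts. Ascertain it in both arms from the same sources on the same schedule: records first, plus one identical dated question about outside stays at 30 and 90 days on the outcome clock (the compensation dates run from enrolment). Report completeness by arm, and study-hospital-only readmission as a sensitivity analysis.

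**Clock.** Do not count readmissions before randomization. Start the 30- and 90-day clocks in both arms at the later of discharge and randomization, and report the discharge-based window as a sensitivity analysis. Amend Study duration to agree with Key inclusion criteria, Procedures and the Consent Process overview.

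**Population.** Reconcile Key inclusion criteria with Basic Info, Target population and Procedures on outside index stays.

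**Cost.** Wording changes across these sections, one question asked twice, record requests for reported outside stays, and two sensitivity analyses. There are two real downsides. Outside stays would be partly self-reported, and capture could become unequal, because the trial is unblinded and only the telehealth arm has daily contact; this is why records come first and completeness is reported by arm. For late enrollees, the window would no longer start at discharge, which changes what is estimated.

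If the sponsor wants a study-hospital-only outcome, saying so consistently removes the contradiction, but outside stays then remain uncounted.
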